### **1.2. Patient enrollment**

We enrolled intubated COPD patients who were newly admitted to the intensive care unit of Changhua Christian Hospital (Changhua, Taiwan). A diagnosis of COPD was defined as audible expiratory wheezing or rhonchus or obstructive ventilatory impairment when assessed by spirometry, in addition to a history of smoking or exposure to other forms of toxic stimuli. All of the enrolled patients were endotracheally intubated and had been mechanically ventilated for less than 72 h. The exclusion criteria were: (1) age less than 18 years, (2) confirmed history of asthma, (3) an Acute Physiology and Chronic Health Evaluation II score of more than 35, and (4) comorbid septic shock. The study was approved by the Institutional Review Board of Changhua Christian Hospital (approval No. 120703). Informed consent was obtained from the surrogates of all participants. All of the participants were randomly assigned to the personalized-dosing or fixed-dosing group according to a computer-generated allocation sequence in a block size of four patients.

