### **1.3. $R_{aw}$ determination**

The enrolled patients were ventilated with either an AVEA® (CareFusion, Yorba Linda, CA, USA), e500 (Newport Medical Instrument Inc. CA, USA), or Evita® 4 (Dräger, Lubeck, Germany) ventilator. When evaluating  $R_{aw}$ , the ventilator settings were transiently switched to volume control

mode with a fixed tidal volume (500 ml) and constant flow (with a rate of 60 L/min). Plateau pressure was measured using a manually controlled end-inspiratory pause lasting for 0.5–1.0 s by qualified respiratory therapists [11]. Consistent with several previous clinical studies [12, 13], our patients were not routinely sedated before  $R_{aw}$  measurements. We made every effort to ensure that the patients were calm during the measurements, including additional sedation if necessary. Each measurement was repeated three times with an interval of at least 1 min, and the average value was calculated.  $R_{aw}$  was calculated using the equation (peak inspiratory pressure – plateau pressure)/flow [14]. After each measurement, the ventilator was set to its usual settings. Thereafter,  $R_{aw}$  was routinely determined every 8 h until the discontinuation of ventilation or the 28th day of the study.

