### **1.7. Outcome measurements**

The primary outcome was the deviation of  $R_{aw}$  from the personal target, which was calculated as  $(\text{measured } R_{aw} - \text{target } R_{aw})/\text{target } R_{aw}$ . The evolution of this deviation over the treatment course was also calculated. The secondary outcomes included the number of ventilator-free days from day 1 to day 28, the percentage of breathing without assistance by day 28, the number of episodes of nosocomial pneumonia, the total number of puffs of rescue short-acting bronchodilators, the number of drug-related adverse effects (arrhythmia or hypokalemia with a Naranjo score [17] of more than 4), and the mortality rate at day 180.

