### **1.8. Statistical analysis**

Data were expressed as number (percentage), mean  $\pm$  standard deviation or median, inter-quartile range (IQR). Each variable was tested for normal distribution using the Kolmogorov-Smirnov test. To compare two continuous variables, we used the Student's *t*-test or the Wilcoxon rank sum test depending on their distribution. For categorical variables, we used the chi-square test or Fisher's exact test as appropriate. A general linear mixed regression model was used to analyze the relative deviation of  $R_{aw}$  over time. This model included fixed effects for the personalized-dosing group, time, and an interaction term of group-by-time, as well as a random intercept and slope. Different durations of stay were considered as the random slope. A *P* value  $<0.05$  was considered to be statistically significant. All statistical analyses were performed using SPSS software (IBM SPSS

Statistics, version 20, IBM Corporation, Chicago, IL, USA). The power of calculating the difference in mean  $R_{aw}$  deviation was 100% with a sample size of 51 and an alpha value of 0.05.

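### Is the 100% power figure at odds with the mixed model used for Raw deviation?

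*Combined protocol and SAP*

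**What the plan says.** Section 1.7 opens with "The primary outcome was the deviation of" Raw from the personal target, expressed relative to that target. It then adds: "The evolution of this deviation over the treatment course was also calculated". It gives no time point and no per-patient summary. Under section 1.3, Raw "was routinely determined every 8 h until the discontinuation of ventilation" or day 28, so each patient contributes a series of readings.

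Section 1.8 offers two kinds of analysis. One is a general rule for continuous variables: Student's t-test or the Wilcoxon rank sum test, depending on distribution. The other is longitudinal: "A general linear mixed regression model was used to analyze the relative deviation of" Raw over time, with fixed effects for group, time and their interaction, plus a random intercept and slope. The section closes with "The power of calculating the difference in mean" Raw "deviation was 100% with a sample size of 51 and an alpha value of 0.05". It gives no difference, SD, test or time origin, and does not say whether 51 is the total or the number per arm.

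**The concern.** A random slope implies numeric time. With numeric time counted from the first reading, the model's group row estimates the gap between arms at the start and its interaction row estimates how fast the gap changes. The power sentence concerns a difference in means, which is neither row. In a randomised trial where extra doses are triggered by later readings, the arms should be about equal at the first reading, so the group row might look empty of treatment effect. If that row were reported as the primary result, a real mean benefit could be missed while the plan's only power figure suggested that this was impossible. The same could happen with the interaction row if the benefit were immediate and constant.

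**Working it through.** **1. The plan's figure.** The 100% can be neither reproduced nor refuted, because no difference or SD is given. Treat the standardised difference d as unknown and assume a two-sided 0.05 t-test with 1:1 allocation. The noncentrality is d / sqrt(1/n1 + 1/n2). For 25 v 26 this is 3.570 × d, with 49 degrees of freedom.

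| d | 51 in total (25 v 26) | 51 per arm |
|---|---|---|
| 0.5 | 41.7% | 70.6% |
| 0.8 | 79.9% | 97.9% |
| 1.0 | 93.8% | 99.9% |

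Power reaches 99.5%, which could be rounded to 100%, at d = 1.296 with 51 in total and at d = 0.907 with 51 per arm. The figure is possible if the effect is large.

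**2. What the model estimates.** The gap between arms at time t is b_group + b_int × t. At t = 0 it is b_group. Averaged over readings with mean time m it is b_group + b_int × m. If time is centred at m, the group coefficient is that average gap. Under any coding it can be estimated from the fitted model.

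**3. The two extremes.** Assumed values, none from the documents: 25 v 26 patients, intercept SD 0.3, slope SD 0.06 per day, residual SD 0.3, readings every 8 h for 7 days in every patient, mean gap 0.5. The standard errors are 0.091 (group), 0.019 (interaction) and 0.104 (average gap).

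- Constant gap: b_group = 0.5, and 0.5/0.091 = 5.5, so power is about 100%. Since b_int = 0, the interaction rejects 5% of the time.
- Gap zero at time 0 and widening linearly: b_int = 0.5/3.5 = 0.143, and 0.143/0.019 = 7.5, so power is about 100%. Since b_group = 0, the group term rejects 5% of the time.
- Average gap in both cases: 0.5/0.104 = 4.8, power 99.8%.

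Each 5% is alpha itself, returned because that coefficient was set to zero. In each case the other coefficient carries the effect.

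**4. Do equal arms at the start empty the group row?** The group coefficient is the intercept of a fitted line, not the observed gap at the first reading. Keep the same assumptions and mean gap of 0.5, but set the gap to zero at the first reading only and constant afterwards.

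- 7 days (22 readings): the group coefficient is 0.435, or 87% of the mean gap. 0.435/0.091 = 4.8, power 99.8%.
- 14 days (43 readings): it is 0.466, or 93%. 0.466/0.088 = 5.3, power about 100%.

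If the gap starts only at 24 h, power is 0.304/0.091 = 3.3, about 92%, at 7 days and over 99% at 14 days. It falls for short courses: about 71% at 5 days and 15% at 3 days.

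**5. The texts side by side.** Section 1.7 names the deviation as primary and lists its evolution as an additional calculation. Section 1.8 has a two-sample rule for continuous variables and a model described as being for deviation over time. Matching the first with the first and the second with the second gives a t-test or rank test for mean deviation and a mixed model for evolution. A power statement about a difference in means then belongs to the t-test.

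**The case for a change.** The strongest reply is that the plan never makes that pairing. The two-sample rule is generic, its Wilcoxon branch does not test means, and a t-test on repeated 8-hourly readings needs one value per patient, which is not defined. Several tests could therefore serve as primary, and the cure looks cheap: name one and tie the power to it.

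Much of this stands. The deciding test, the per-patient summary, the time origin, the inputs to the 100% and the meaning of 51 are all unstated. The 100% should not be attached to the group or interaction row. The figure may also have been computed from observed data; the documents do not say. If so, 99.5% or more at 25 v 26 would correspond to |t| of at least 1.296 × 3.570 = 4.63, and it would only restate the p-value.

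These are omissions, though, and do not amount to a conflict between the power statement and the model. Powering on a t-test with a rank-test fallback is common practice, and the mean of a patient's readings is an obvious summary. Nothing in the plan makes either model row the primary result. The obvious repair, a contrast at the mean reading time, is not clearly better: that time depends on how long patients stay ventilated, which treatment may change, and ventilator-free days are themselves a secondary outcome.

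**Conclusion.** No change to the plan follows. The algebra is right: with uncentred time, neither treatment coefficient of the mixed model is the mean difference. The mismatch with the power sentence further requires the mixed model to be the primary test, and the documents state neither condition. On the natural reading of sections 1.7 and 1.8, the power sentence and the t-test agree.

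The 5% figures describe exact extremes. With a step effect from the second reading, the group term keeps over 99% power for 7- and 14-day courses; with onset at 24 h and short courses it can be much weaker. These results rest on the variances, the common course lengths and the mean gap of 0.5 assumed above. The 100% itself is not shown to be wrong. What remains is missing detail that analysts can fill sensibly by reporting mean deviation per patient and using the model for the time course.
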